4.2.2.2 Assessment of Compliance

Accountability and subject compliance will be assessed by maintaining adequate drug dispensing and return records. Subjects will be instructed on how to self-inject at the screening visit and re-instructed at each visit if deemed necessary by the Investigator/delegate.

A Drug Inventory/Dispensing Log provided by Roche must be kept current and should contain the following information at a minimum:

Recormon—F. Hoffmann-La Roche Ltd

Protocol ML29005, Version 3.0 dated 12 Sep 2016

26

- the identification of the subject to whom the study medication was dispensed
- the date[s], quantity of the study medication dispensed to the subject
- the initials of the person confirming administration of the study medication
- the date[s] and quantity of the study medication returned by the subject

This inventory must be available for ongoing inspection by the Monitor. In case of home administrations, for assessment of compliance, subjects will be asked to return all used and unused drug supply boxes to the investigational site at each visit. The compliance will be assessed by reconciliation of the number of unused syringes and empty drug supply boxes returned. Immediately after self-injection by the subject, the used syringes must be placed in a safety container provided by Roche. This safety container should be returned to the investigational site at each visit for immediate disposal by site staff in accordance with the study site's institutional standard operating procedure

4.2.3 Investigational Medicinal Product Accountability

Recormon® will be provided by the Sponsor. The investigational site will acknowledge receipt of IMPs to confirm the shipment condition and content. Any damaged shipments will be replaced.

IMPs will either be disposed of at the study site according to the study site's institutional standard operating procedures or returned to the Sponsor with the appropriate documentation. The site's method of IMP destruction must be agreed upon by the Sponsor. The site must obtain the written authorization from the Sponsor before any IMP is destroyed, and IMP destruction must be documented on the appropriate form.

Accurate records of all IMPs received at, dispensed from, returned to, and disposed of by the study site should be recorded on the Drug Inventory Log.

4.2.4 Post-study Access to Recormon®

The Sponsor will offer post-study access to the study drug (Recormon®) free of charge to eligible patients in accordance with the Roche Global Policy on Continued Access to Investigational Medicinal Product, as outlined below.

A patient will be eligible to receive study drug after completing the study if all of the following conditions are met:

- The patient has a life-threatening or severe medical condition and requires continued study drug treatment for his or her well-being
- There are no appropriate alternative treatments available to the patient
- The patient and his or her doctor comply with and satisfy any legal or regulatory requirements that apply to them

A patient will not be eligible to receive study drug after completing the study if any of the following conditions are met:

- The study drug is commercially marketed in the patient's country and is reasonably accessible to the patient (e.g., is covered by the patient's insurance or wouldn't otherwise create a financial hardship for the patient)
- The Sponsor has discontinued development of the study drug or data suggest that the study drug is not effective for low/intermediate-1 risk MDS
- The Sponsor has reasonable safety concerns regarding the study drug as treatment for low/intermediate-1 risk MDS
- Provision of study drug is not permitted under the laws and regulations of the patient's country

The Roche Global Policy on Continued Access to Investigational Medicinal Product is available at the following Web site:

http://www.roche.com/policy_continued_access_to_investigational_medicines.pdf

4.3 CONCOMITANT THERAPY

4.3.1 Permitted Therapy

Concomitant therapy includes any medication (e.g., prescription drugs, over-the-counter drugs, herbal/homeopathic remedies, nutritional supplements) used by a patient from 4 weeks prior to screening to the end-of-study visit/early termination visit.

Throughout the study, patient could be treated with any concomitant medications or treatment necessary to provide adequate supportive care except for those treatments listed in the prohibited therapy. Upon physician discretion and their normal practice, G-CSF can be used.

All RBC transfusions administered during the study should be documented (i.e., specified by number of units transfused) and recorded on the eCRF.

All concomitant medications should be reported to the investigator and recorded on the Concomitant Medications electronic Case Report Form (eCRF).

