- Absolute increase of $\geq 30 \times 10^9/L$ for patients starting with $> 20 \times 10^9/L$ platelets (Increase from $< 20 \times 10^9/L$ to $> 20 \times 10^9/L$ and by at least 100%)
- % patients with neutrophil response (pre-treatment $< 1.0 \times 10^9/L$) at week 12 defined by IWG 2006 as following;
- At least 100% increase and an absolute increase $> 0.5 \times 10^9/L$

Safety Outcome Measures

The safety outcome measures for this study are as follows:

- Tolerability and safety of Recormon®

Investigational Medicinal Products

Injectable solution of Recormon® (provided free of charge by Roche) 30,000 or 60,000 IU per week administered subcutaneously

The initial dose is 30,000 IU per week administered subcutaneously

- Response will be firstly evaluated at week 4 (visit 2):
 - If haemoglobin level ≥ 12 g/dL at any time, Recormon® should be discontinued until Hb levels are ≤ 10 g/dL
 - If the haemoglobin level increases < 1 g/dL from screening level and haemoglobin level < 12 g/dL, a 60,000 IU weekly of Recormon® will be administered subcutaneously until week 12
 - If the haemoglobin level increases ≥ 1 g/dL from screening level and haemoglobin level < 12 g/dL, a 30,000 IU weekly of Recormon® will be continued until week 12

Non-Investigational Medicinal Products

Upon physician discretion, G-CSF can be used concurrently

Statistical Methods

Descriptive statistics will be used for baseline characteristics. The interim data analysis will be performed when the first 30 patients completing 12-week treatment period.

Determination of sample size

Sample size based on a 5% significance level and the 80% power with 10% drop out resulting of 120 patients in total.

Safety: Assuming a 10% withdrawal rate, 120 patients will be enrolled such that we expect 108 patients will not withdraw and will remain evaluable. With 108 evaluable patients in this study, the sample size is sufficient to have at least 95% probability of observing a particular adverse event in at least one patient in this study, if the true proportion of patients in the target population as a whole who experience this event is 0.0274 i.e. approximately 1 in every 37 patients.

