3. STUDY DESIGN

3.1 DESCRIPTION OF STUDY

3.1.1 Overview of Study Design

This is a phase IV, prospective, multi-centre, open label study to assess the efficacy of Recormon® for treating anemic patients with low/intermediate-1 risk MDS, in approximately 120 adult patients. The primary efficacy endpoint is a proportion of patients achieving erythroid response at week 12 according to IWG 2006 definition. The trial will be conducted at approximately 8 centres nationwide.

All potential study patients must provide signed written informed consent approved by the relevant independent Ethics Committee before undergoing any study-specific procedures. Results of the screening assessments must be available and patients must meet all eligibility criteria prior to enrolment into the study. The study design is shown in Figure 1.

[figure not shown]

Figure 1 Study Scheme

The study consists of a 2-week screening period, a 12-week treatment phase and end-of-study visit (see figure 1). After screening, eligible patients will be treated with epoetin beta (Recormon®) as recommended in the approved label and international guidelines for the use of epoetin in MDS patients, Recormon® dosage will be adjusted on the basis of erythroid response.

During screening period, serum level of endogenous erythropoietin will be assessed, as well as liver and kidney function. Bone marrow morphology analysis and karyotyping are also performed during screening if they have not been assessed in the 6 months prior to participation in the study. Complete blood count test is performed during screening period and at every patient's visit until the end of study visit. The result should be available prior to dosing of Recormon®.

The patient's erythroid response will be assessed at week 4 and every 4 weeks thereafter, until end-of-study visit. Patients who achieve Hb level ≥ 12 g/dL will stop treatment, while

Recormon—F. Hoffmann-La Roche Ltd

Protocol ML29005, Version 3.0 dated 12 Sep 2016

23

patients with Hb level < 12 g/dL will continue treatment for the total of 12 weeks. Concurrent G-CSF can be administered upon physician discretion.

Patients can withdraw from the study at any time as per section 4.5.1

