3.4 OUTCOME MEASURES

3.4.1 Efficacy Outcome Measures

The efficacy outcome measures for this study are as follows:

Primary Efficacy Outcomes:

- The cumulative proportion of patients achieving erythroid response at week 12 according to IWG 2006 definition as
 - Hb increase by ≥ 1.5 g/dL
 - Reduction of units of RBC transfusions by an absolute number of at least 4 RBC transfusions/8 weeks compared with the pre-treatment transfusion number in the previous 8 weeks. Only RBC transfusions given for a Hb of ≤ 9.0 g/dL pre-treatment will count in the RBC transfusion response evaluation

Secondary Efficacy Outcomes:

- % patients with platelet response (pre-treatment $< 100 \times 10^9/L$) at week 12 defined by IWG 2006 as following:
 - Absolute increase of $\geq 30 \times 10^9/L$ for patients starting with $> 20 \times 10^9/L$ platelets (Increase from $< 20 \times 10^9/L$ to $> 20 \times 10^9/L$ and by at least 100%)
- % patients with neutrophil response (pre-treatment $< 1.0 \times 10^9/L$) at week 12 defined by IWG 2006 as following;
 - At least 100% increase and an absolute increase $> 0.5 \times 10^9/L$

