4.1.1 Inclusion Criteria

Patients must meet the following criteria for study entry:

- Able and willing to provide written informed consent and to comply with the study protocol
- Adult patients (≥ 18 years old)
- Low or intermediate-1 risk MDS (having IPSS risk score ≤ 1) confirmed with bone marrow morphology analysis and karyotyping within 6 months prior to screening
- No previous treatment with hematopoietic growth factors within 3 months prior to screening
- Symptomatic anemia ($Hb < 10 \text{ g/dL}$) as determined by investigator
- Serum Erythropoietin $< 500 \text{ mU/ml}$ within 14 days prior to the first dose of study treatment
- Require no red blood cell transfusion or dependent on < 4 units within 8 weeks prior to screening
- Clinically stable for at least one month prior to entry into the study as determined by investigator
- For female patients of childbearing potential and male patients with partners of childbearing potential, agree (by patient and/or partner) to use highly effective form(s)

Recormon—F. Hoffmann-La Roche Ltd

Protocol ML29005, Version 3.0 dated 12 Sep 2016

25

of contraception (i.e., one that results in a low failure rate [$< 1\%$ per year] when used consistently and correctly)

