4.3.2 Prohibited Therapy

The following treatments are prohibited during study treatment:

Investigational or unlicensed/unapproved agents of any type

Patients receiving any of the prohibited therapies will be discontinued and assessed for safety at end-of study visit

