6.4.2 Secondary Efficacy Endpoints

Secondary efficacy endpoints include platelet and neutrophil response at week 12, defined by the following IWG 2006 criteria and will analyzed for the PP population.

- % patients with platelet response (pre-treatment $< 100 \times 10^9/L$) at week 12 defined by IWG 2006 as following:
 - Absolute increase of $\geq 30 \times 10^9/L$ for patients starting with $> 20 \times 10^9/L$ platelets (Increase from $< 20 \times 10^9/L$ to $> 20 \times 10^9/L$ and by at least 100%)
- % patients with neutrophil response (pre-treatment $< 1.0 \times 10^9/L$) at week 12 defined by IWG 2006 as following:
 - At least 100% increase and an absolute increase $> 0.5 \times 10^9/L$

The percentages of patient who achieve the above hematologic responses at week 12, according to the IWG 2006 criteria will be presented in summary tables.

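### Neutrophil response is judged by the count alone while G-CSF is permitted, so G-CSF-driven rises are pooled into a Recormon efficacy outcome

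*Protocol*

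**What the plan says.** **The endpoint.** Section 3.4.1 lists, among the secondary efficacy outcomes, the percentage of "patients with neutrophil response (pre-treatment" count below 1.0 x 10^9/L) at week 12. Section 6.4.2 repeats the criterion: "At least 100% increase and an absolute increase" of more than 0.5 x 10^9/L. It adds that the secondary endpoints "will analyzed for the PP population" and that the percentages will appear in summary tables. Neither section mentions G-CSF.

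**G-CSF on study.** Use is allowed in three places:
- section 3.1.1: "Concurrent G-CSF can be administered upon physician discretion";
- section 4.3.1: "Upon physician discretion and their normal practice, G-CSF can be used";
- the synopsis, under non-investigational products: "Upon physician discretion, G-CSF can be used concurrently".

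None of them limits timing or duration. The only prohibited therapy in section 4.3.2 is "Investigational or unlicensed/unapproved agents of any type".

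**G-CSF before study.** Section 4.1.1 requires "No previous treatment with hematopoietic growth factors within 3 months prior to screening".

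**Duration.** Sections 3.4.1 and 6.4.2 refer to IWG 2006. In the protocol's own IWG table (Appendix 3), the column of haematological improvement criteria, neutrophil included, is headed with a duration of at least 8 weeks. Sections 3.4.1 and 6.4.2 give only the week-12 time point.

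**The concern.** G-CSF is given to raise granulocytes, and this endpoint asks whether neutrophils rose. The pre-treatment count is free of recent growth factor, so any G-CSF started on study falls between the two counts being compared. All patients receive Recormon and there is no comparator, so nothing in the design can subtract the G-CSF contribution.

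Such use is foreseeable from the protocol's own background. Section 1.1 says growth-factor support, G-CSF included, should be considered for symptomatic low counts that persist after other causes are corrected. Section 1.3 says adding G-CSF is suggested when a patient does not respond to the ESA. The patients eligible for this endpoint are those who start with low neutrophils, so they are plausible candidates.

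At stake is whether one reported efficacy percentage can be interpreted. The primary endpoint's definition and the sample size do not depend on it.

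**Working it through.** The protocol states no planning figure for this endpoint. Its stated figures concern other quantities, and they reproduce:
- evaluable patients: 120 x 0.90 = 108;
- 95% interval half width for an erythroid response of 0.25: 1.96 x sqrt(0.25 x 0.75 / 108) = 0.0817.

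**1. What count meets the written rule.** From a start of x (below 1.0, in 10^9/L), the week-12 count must be at least 2x and also exceed x + 0.5.
- x = 0.3: above 0.8
- x = 0.5: above 1.0
- x = 0.7: at least 1.4
- x = 0.9: at least 1.8
- x approaching 1.0: the requirement approaches 2.0

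The cause of the rise does not enter the rule.

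**2. What the Appendix 3 duration would change.** Appendix 1 schedules counts at weeks 0, 4, 8 and 12. If the 8 weeks must be complete by week 12, the rise must be present from about week 12 - 8 = 4 onward, within the 1-week visit windows. A short or late G-CSF course would then not qualify, but sustained use from early in the study still could. If only the text of 3.4.1 and 6.4.2 governs, the week-12 count alone decides.

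**3. How the pooled rate behaves.** Among eligible patients, let g be the share given G-CSF, r the response rate with it and b the rate without it.

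Pooled rate = (1 - g)b + g r, which exceeds b by g(r - b).

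The protocol gives none of the three, so these are assumed values:
- b = 0, g = 10%, r = 50%: 0.10 x 0.50 = 5%
- b = 0, g = 50%, r = 90%: 0.50 x 0.90 = 45%
- b = 5%, g = 30%, r = 60%: 0.70 x 0.05 + 0.30 x 0.60 = 21.5%
- b = 5%, g = 30%, r = 90%: 0.70 x 0.05 + 0.30 x 0.90 = 30.5%

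In the third case the rate without G-CSF is 5%. The overall rate is 3.5% (0.70 x 0.05) with G-CSF recipients as non-responders, and 21.5% unadjusted. One pooled percentage hides that spread.

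**4. Weight of one patient.** The number starting below 1.0 is not given.
- If 10% of 108 do: 10.8, about 11 patients, and one G-CSF-driven responder moves the rate by 1/11 = 9.1 points.
- If 30% do: 32.4, about 32 patients, and the shift is 1/32 = 3.1 points.

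**5. Whether the per-protocol set removes these patients.** Permitted G-CSF is not a prohibited therapy under 4.3.2, so its use is not in itself a violation. Section 6.2 defines only the ITT and safety populations, and section 6.4.1 sends the evaluability criteria to the analysis plan. Nothing in the protocol takes G-CSF recipients out.

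**The case against.** **Treatment policy.** This is a phase IV effectiveness study with G-CSF allowed as normal practice, and the only efficacy objective is erythroid response. A rate under Recormon with whatever supportive care was given is a legitimate summary. That stands as a description. It does not make the pooled figure readable as response to Recormon, and the outcome is listed as efficacy of Recormon, with G-CSF classed as non-investigational.

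**The analysis plan.** Handling of a permitted drug, and per-protocol evaluability, may be settled in a plan not shown. This stands in part: that plan may exclude or separate G-CSF recipients. But the protocol itself fixes the responder rule and the single percentage. Its only opening, an optional subgroup analysis in section 6.4, does not name G-CSF.

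**Duration.** A reader might infer that any eligible patient whose count reaches 2.0 x 10^9/L at week 12 is a responder. The documents do not settle that. It follows from 3.4.1 and 6.4.2 read alone, but the Appendix 3 heading would require a sustained rise. The duration narrows the mechanism without removing it.

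**Counting every G-CSF recipient as a non-responder.** As the sole main rule this would add its own distortion. Section 1.3 links G-CSF to poor erythroid response, so patients could be marked down on neutrophils for an erythroid reason, and a true Recormon effect in them would be lost. This objection stands. It favours showing the rate by G-CSF use, with the non-responder version only as a companion figure.

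**Conclusion.** The point holds. As written, a G-CSF-driven rise that meets the count rule is included in a Recormon efficacy outcome and cannot be separated in a single-arm, pooled summary. The direction is clear wherever G-CSF raises the chance of meeting the rule: the pooled rate then exceeds the rate without G-CSF.

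The size is not known. A reader might take the 5% to 45% range as an estimate of the bias. It is only the product of assumed shares, with Recormon assumed to have no effect, and would be smaller if the 8-week duration in Appendix 3 leaves few qualifying G-CSF rises. The weight is modest: the endpoint is secondary and descriptive, and no sample-size figure, interim analysis or stated objective rests on it.

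**What to change.** In sections 3.4.1 and 6.4.2, and in the matching synopsis text, state that:
- the neutrophil response rate will be reported separately for patients who did and did not receive G-CSF before the week-12 assessment, with the number in each group;
- only the rate without G-CSF is to be read as response on Recormon;
- the overall rate will be shown beside it in two forms, unadjusted and with G-CSF recipients counted as non-responders.

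This works under either reading of the duration and proposes no change to permitted treatment.

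The cost is a few sentences and one further table. Concomitant medications are already recorded on the eCRF under section 4.3.1, but G-CSF start dates must be available. The split gives a smaller denominator, and the non-responder version a lower rate. The group without G-CSF is also self-selected, since physicians decide who receives it, so its rate is easier to interpret but not free of selection.

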1.3 STUDY RATIONALE AND BENEFIT–RISK ASSESSMENT

Chronic refractory anemia and long-term use of blood transfusions pose a tremendous clinical and economic burden to the management of MDS patients. Thus, treatment options aimed at maintaining transfusion independence or delaying transfusion dependence play an important role in the management of low-risk early disease.

Of the currently available therapeutic options, Erythropoiesis-stimulating agents (ESAs) alone or in combination with GCSF appear to fulfill this goal in a significant proportion of MDS patients. In contrast to the application of these growth factors to treat the side effects of chemotherapy in other cancers, their use in MDS appears to serve a therapeutic role since ineffective hematopoiesis, and specifically defective erythropoiesis, constitute the basic pathology in MDS. By promoting survival and differentiation ESAs overcome excessive apoptosis of erythroid progenitors and, hence, are therapeutic in alleviating the basic pathology of these disorders.

Recombinant erythropoietin (EPO) can correct anaemia in about 20% of MDS when used alone and 40% when combined with recombinant human granulocyte colony-stimulating factor (G-CSF), and the response rate to EPO + G-CSF is higher than that of symptomatic treatment (Economopoulos et al. 1999, Remacha et al. 1999, Hellstrom-Lindberg et al. 2003, and Casadevall et al. 2004). Major prognostic factors for a favourable response to EPO ± G-CSF are low endogenous serum EPO levels (<200 or 500 U/l) and relatively low transfusion requirement. In patients with a serum EPO level below 500 U/l, response rates to EPO + G-CSF reach 60% (Hellstrom-Lindberg et al. 2003 and Casadevall et al. 2004).

Result from prospective randomized phase III trial by the Eastern Cooperative Oncology Group (E1996) confirm earlier studies by demonstrating the efficacy of adding G-CSF to EPO and higher EPO dose for enhancing erythroid responses in MDS (Greenberg et al. 2009). Mo yo et al. (Mo yo et al. 2007) also suggest increasing EPO dose may have a greater impact on erythroid responses than addition of G/GM-CSF.

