controlled trial with ESA in MDS conducted thus far showed that the patients treated with EPO as a single agent had numerically lower rates of adverse events (32%) compared with those on placebo (43%) (ITALIAN COOPERATIVE STUDY GROUP 1998). Furthermore, encouragingly, no treatment-related episodes of thrombosis or seizures were reported in this trial or even after long-term administration of EPO to MDS patients in another large, single-arm trial (Terpos et al. 2002). The noticeable absence of therapy-related thrombotic events with EPO treatment of MDS in several clinical trials so far is indeed distinguished from even the minimum acceptable risk of thrombotic complications of ESAs when used in chemotherapy-induced anemia as listed in the drug prescribing information for epoetin- α or darbepoetin- α . Thus, treatment of MDS with ESA in general seems to be well tolerated with significant clinical benefits in MDS.

ESA use in MDS is widespread; recent estimates suggest that 60% of MDS patients received ESAs (Sekeres et al. 2008). The last update of the 2011 National Comprehensive Cancer Network guidelines (Greenberg et al. 2011) acknowledges the fact that anemia is a major issue in MDS patients to be addressed even more carefully than in the past with parallel statements by the Italian Society of Hematology (Alessandrino et al 2002), the United Kingdom (UK) MDS Guidelines Group (Bowen et al. 2003), Nordic MDS Group (Guideline by NMDS group), and the Thai MDS study group (Guideline by The Thai Society of Hematology).

As improvements in haemoglobin are usually noted 6–8 weeks after initiation of an adequate dose of ESA, a minimum 8-week therapeutic trial was considered to be indicated. Moreover, it should be noted that ESA doses found to impact the anemia of MDS are substantially higher than those used in chronic renal insufficiency (Oliva et al. 2010). The addition of granulocyte colony-stimulating factor (G-CSF), thought to synergize with ESA in producing an erythropoietic effect in MDS patients, is suggested for patients who do not manifest a response to ESA (Jadersten et al. 2008 and Hellstrom-Lindberg et al. 2003).

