2. OBJECTIVES

2.1 EFFICACY OBJECTIVES

The primary efficacy objective for this study is:

- To assess the efficacy of Recormon® for treating anemic patients with low/intermediate-1 risk MDS, as measured by erythroid response

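### The single-arm primary response rate describes Recormon with or without G-CSF, but the objective attributes it to Recormon

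*Protocol*

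**What the plan says.** Section 2.1 gives one efficacy objective: "To assess the efficacy of Recormon® for treating anemic patients with low/intermediate-1 risk MDS, as measured by erythroid response". Section 1.3 explains the need for the study by the scarcity of published data on epoetin beta.

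On co-treatment, section 4.3.1 says "Upon physician discretion and their normal practice, G-CSF can be used". The synopsis and section 3.1.1 repeat the permission, and none of these places sets a rule on timing or indication. Section 4.3.1 also allows that a "patient could be treated with any concomitant medications or treatment necessary to provide adequate supportive care except for those treatments listed in the prohibited therapy". The whole prohibited list in 4.3.2 is "Investigational or unlicensed/unapproved agents of any type". At entry, section 4.1.1 requires "No previous treatment with hematopoietic growth factors within 3 months prior to screening"; there is no matching rule once treatment has begun.

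On the size of a G-CSF effect, section 1.3 states that EPO "can correct anaemia in about 20% of MDS when used alone and 40% when combined with recombinant human granulocyte colony-stimulating factor". It adds that G-CSF is thought to act in synergy with ESAs and "is suggested for patients who do not manifest a response to ESA".

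On analysis, sections 6.2 and 6.4 define the efficacy population as all enrolled patients with at least one dose. Section 6.4.1 tabulates the percentage meeting the haemoglobin or transfusion criterion. Section 6.4 makes subgroup analysis optional and does not name G-CSF.

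**The concern.** There is no control arm, so nothing absorbs the effect of co-treatment. The response criteria in 3.4.1 look only at haemoglobin and transfusions, so a response reached with the help of G-CSF enters the numerator on equal terms with a response to Recormon alone. The protocol's own background says the added drug acts on the primary endpoint.

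Two trials with the same Recormon effect could therefore report different rates because their sites differ in how readily they add G-CSF. For a study meant to add evidence on epoetin beta, that weakens the one number it is designed to deliver. A reader who sets the result beside the 20% or the 40% quoted in section 1.3 would not know which is the right comparator.

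**Working it through.** **Inputs**
- Planning rate 0.25 with 108 evaluable patients; stated half-width 0.0817 (section 6.1).
- Response with EPO alone 0.20 and with EPO plus G-CSF 0.40, for MDS in general (section 1.3).
- Share of patients given G-CSF, *f*: not stated, so the full range from 0 to 1 is considered.

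**Step 1: the protocol's precision figure.** 1.96 × √(0.25 × 0.75 / 108) = 0.0817, interval 0.1683 to 0.3317. This agrees with section 6.1.

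**Step 2: pooled rate by uptake.** If the patients given G-CSF respond at 0.40 and the rest at 0.20:

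pooled = 0.20(1 − f) + 0.40f = 0.20 + 0.20f, so the excess over EPO alone is 0.20f.

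| Uptake f | Pooled rate | Excess |
|---|---|---|
| 0% | 0.20 | 0 |
| 10% | 0.22 | 0.02 |
| 20% | 0.24 | 0.04 |
| 25% | 0.25 | 0.05 |
| 50% | 0.30 | 0.10 |
| 100% | 0.40 | 0.20 |

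**Step 3: comparison with the planned precision.** The excess equals the half-width when 0.20f = 0.0817, that is f = 0.41. At f of about 0.43 the pooled rate is 0.285 and the lower 95% limit with 108 patients is 0.200, so from there the interval would exclude the EPO-alone rate.

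**Step 4: what the reported number cannot separate.** The planning example of 0.25 would arise from a true Recormon-alone rate of 25% with no G-CSF use. It would also arise from a rate of 20% with a quarter of patients on G-CSF (0.20 + 0.20 × 0.25 = 0.25).

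**Step 5: sensitivity to who receives G-CSF.** Step 2 treats G-CSF patients as an average subset. If instead G-CSF went only to failures of EPO alone, a conversion rate among failures is needed, and the protocol gives none. Assume that the move from 20% to 40% is 20 conversions among 80 failures, or 25%. Then pooled = 0.20 + 0.25f for f up to 0.80. This gives 0.25 at 20% uptake and 0.325 at 50%, and the half-width is reached at 0.0817 / 0.25 = 33%.

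**Step 6: do 20% and 40% apply here?** The trial enrols low or intermediate-1 risk patients with serum EPO below 500 mU/ml and fewer than 4 units transfused in 8 weeks. For selected patients, section 1.3 cites 60% with EPO plus G-CSF, and nearly 60–65% for ESAs without separating G-CSF use. No EPO-alone rate for this population can be taken from those figures, so the excess here could be smaller than in Step 2, even close to nil.

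**The case against.** The case on the other side has real weight. This is an open-label phase IV study whose title speaks of effectiveness, and the synopsis openly lists G-CSF as a non-investigational product. Counting every dosed patient under permitted background care is a recognised treatment-policy estimate. The analysis is descriptive, and no test against 20% or 40% is planned. Concomitant medication is recorded on the eCRF, and a SAP that is not shown could tabulate its use.

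All of that stands as a defence of the pooled rate as a quantity. It does not justify attributing that rate to Recormon, which is what section 2.1 does. The protocol defers interim details, evaluability criteria and safety details to the SAP (6.3, 6.4.1, 6.5), but not the handling of growth factors. An optional subgroup split by G-CSF use would not settle the matter either. Use begins after baseline, and if it follows non-response the comparison is confounded.

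A reader might go further in three ways that the documents do not support:
- *That G-CSF doubles response in this trial.* The 20% and 40% are for MDS in general, and section 1.3 ties the figure of about 20% to earlier use in unselected patients. It also cites a suggestion that raising the EPO dose may matter more than adding a growth factor.
- *That Recormon failures are systematically turned into successes.* Use after non-response is a literature suggestion in section 1.3, not a study rule. At week 4 the protocol's stated response to a small rise is a change of Recormon dose (4.2.2.1). Appendix 3 heads the improvement criteria with at least 8 weeks, which leaves little room for G-CSF started late to produce a qualifying response by week 12.
- *That other licensed ESAs will be credited to Recormon.* This rests mainly on silence in 4.3.2. No section expressly permits a second ESA, so the point is secondary.

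**Conclusion.** The point holds as a mismatch between the objective and the primary summary. The pooled rate is a valid description of Recormon with or without G-CSF; it is not an estimate of response to Recormon alone, and nothing in the protocol labels it as the former.

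The size cannot be fixed from the document. Under the assumed rates of 20% and 40%, with G-CSF patients an average subset, the excess is 0.20 times uptake. That is negligible against the planned precision at 10% uptake and comparable with it at around 41%. Uptake is an assumption throughout, and the two rates may not carry over to the enrolled population. A reader might conclude that the result says nothing about Recormon; that is too strong, because with low uptake the pooled and Recormon-alone rates would nearly coincide. The difficulty is that the planned table would not show whether this was so.

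**What to change.** In sections 3.4.1 and 6.4.1:
1. Keep the rate over all dosed patients, and label it *Recormon with or without G-CSF*.
2. Report how many patients received G-CSF or another growth factor, with start dates relative to response.
3. Pre-specify a second row in the primary table in which a patient who starts G-CSF, GM-CSF or another ESA before first meeting the criterion counts as a non-responder. Present it as a conservative, lower-bound estimate of response to Recormon alone.
4. Have any efficacy statement about Recormon cite both rates. The second row should not be its sole basis.

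The cost is endpoint wording and a few table entries from the Concomitant Medications eCRF that section 4.3.1 already requires. Permitted care stays as it is. The downside is that the second rate can only be equal to or lower than the first. It may understate Recormon where G-CSF was given for neutropenia, or before a response that would have come late without it. That is why it belongs beside the pooled rate and does not replace it.
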